4.2 Objectives

For stage 1, the primary objective is to evaluate the effect of optimising the BOOST programme on walking capacity as measured by the ODI walking item and the 6-minute walk test. Our primary objective for stage 2 is to again evaluate the effect of the BOOST programme on walking capacity, as measured by the ODI walking item and the 6-minute walk test, when delivered by therapists that have received the BOOST training online via the BOOST MOOC.

Secondary objectives are to:

- Evaluate the effect of the optimised BOOST programme on patient reported pain-related disability, quality of life, physical activity, and satisfaction (stage 1 and 2).
- Interview the therapists delivering the optimised BOOST programme to explore their experiences. The exact number of interviews will depend on the number of staff delivering each group (estimated number: 5).
- Evaluate learning outcomes and implementation intentions on completion of the BOOST MOOC.
- Evaluate therapist self-reported implementation outcomes 6 months after completion of the BOOST MOOC.
- Interview the therapists who have delivered the BOOST programme after completing training via the BOOST MOOC to understand their experiences (estimated number: 10).

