10-point managing symptoms item	X	х				
Satisfaction		х				
Single item physical activity question		x				
Activity over 16 days (wearable)	х	X				
Activity log	х	X				
Sleep efficiency	х	Х				

Therapist participants

All therapist data will be collected during stage 2 using JISC online surveys. Therapist demographics will be collected prior to starting the BOOST MOOC and will include name, email, sex, age, occupation, professional qualification, work setting, years of experience treating symptomatic LSS patients and average number of patients treated per month (if applicable). We will collect learning

outcomes and implementation intentions online at the end of the BOOST MOOC. Learning outcomes include self-reported course completion, perceived confidence (in their own ability) and capability (given wider external factors such as necessary space and equipment) to deliver the BOOST programme. Implementation outcomes align with the taxonomy proposed by Proctor et al (16) and include implementation intention (Adoption), satisfaction with the training (Acceptability) and potential barriers to implementation (Appropriateness) and actual use in practice (Adoption). Therapists will be emailed a link to a brief follow up questionnaire by the study team 6 months after completing the baseline assessment to assess additional implementation outcomes. We will again ask participants about self-reported course completion and actual use in practice (Adoption as well as asking them about the number of BOOST sessions delivered (Fidelity), perceived patient satisfaction with the BOOST programme (Acceptability), perceived clinical usefulness of the BOOST programme, helpful and unhelpful aspects of the BOOST programme with regards to implementation, and reasons for non-implementation (Appropriateness). Outcomes and timepoints are detailed in Table 3.

Table 3: Therapist participant outcomes and assessment time points

	Timepoint				
	Start of	On completion	6 months from		
Stage 2	MOOC	of MOOC	MOOC enrolment		
Informed consent	х				
Therapist demographics	х				
Course completion		х	x		
Satisfaction with training		х			
Confidence to deliver the BOOST programme		х	х		
Capability to deliver the BOOST programme		х	x		
Implementation intention		х	x		
Potential barriers to implementation		x	x		
Actual use in practice		х	x		
Perceived patient satisfaction			x		
Number of BOOST programme cycles delivered			х		
Perceived clinical usefulness of BOOST			x		

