Therapists who manage (or plan to manage) patients with symptomatic LSS in the UK will be invited to participate in a soft launch of the BOOST MOOC. This will not be publicly available, and therapists will need to agree to participate in the cohort study to gain access to it. We will target a minimum of 30 therapists and will recruit them through special interest groups and networks, conferences, University of Exeter, Keele and Oxford research group contact lists, Applied Research Collaboration regional websites, social media platforms, and personal contacts. Interested therapists will be asked to contact the BOOST study team to express their interest. Interested therapists will be sent a link to a webpage containing a participant information sheet, consent form and a baseline questionnaire prior to enrolment in the course. After providing informed consent and completing the baseline questionnaire, therapists

will be sent a link to enrol in the BOOST MOOC with instructions on how to create an account on FutureLearn. Once enrolled, therapists will have full access to the BOOST MOOC content. Therapists will be asked to complete the course within a six-week period from the date of registration.

Therapists who have completed the BOOST MOOC will be invited to participate in a cohort study to evaluate patient outcomes. We will target 10 NHS sites. Site can choose to deliver the BOOST programme within an NHS setting or to partner with a community provider for the delivery of the BOOST programme.

We will email the first 10 therapists to deliver the optimised BOOST programme in their practice to invite them to participate in a semi-structured interview.

Patient participant recruitment

Patient recruitment and study procedures are the same as those described in stage 1 above.

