Therapists expressing an interest in the BOOST MOOC will be emailed a link to a webpage containing the PIS and ICF, detailing the exact nature of the cohort study and informing them that their data will be shared with the BOOST study team. It will be clearly stated that the participant is free to withdraw from the cohort study at any time, for any reason, and with no obligation to give a reason for withdrawal. Data

contributed to the study up until the point of withdrawal will remain with the study group, unless stated by the withdrawing participant.

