Data from the wrist worn accelerometer is stored locally on the device. On receipt of the devices return, the activity informatics team at the University of Exeter will transfer data from the device to their research grade, secure cloud server. Once analysed, the activity informatics team will transfer the pseudo-anonymised output files to the BOOST study team using the University's secure OneDrive. These files will then be downloaded into the University's RDS storage and merged with the remaining study data by the study's statistician. The anonymised monitoring log that participants return with their wrist worn accelerometer will be used to facilitate data analysis by the activity informatics team and will be stored securely in locked filing cabinets at the University of Exeter.

Therapist participants

Data from the BOOST MOOC evaluation will be collected using JISC online surveys. Each participant will have a unique ID that links their anonymised survey responses. Data will be downloaded from JISC and stored securely in the University's RDS platform. Files will only be accessed by designated members of the study team.

Therapist interviews will be conducted on MS Teams and will be audio-video recorded and automatically transcribed. These files will be automatically downloaded to the University of Exeter's cloud-based storage solution (OneDrive) and will be manually moved onto the University's RDS platform for secure storage.

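### Stage 2 course completion is measured only by therapist self-report, and the protocol does not say how it is confirmed before a therapist enters the patient cohort

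*Protocol*

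**What the plan says.** Section 6.1 (Therapist participants) defines the end-of-course learning outcomes: "Learning outcomes include self-reported course completion, perceived confidence (in their own ability) and capability". For the 6-month questionnaire it adds: "We will again ask participants about self-reported course completion and actual use in practice". Table 3 lists course completion at both points and names no other source.

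The source of the data is stated twice. Section 6.1: "All therapist data will be collected during stage 2 using JISC online surveys". Section 9.6.2: "Data from the BOOST MOOC evaluation will be collected using JISC online surveys".

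The same event controls entry to the second part of Stage 2. Section 7.2 (Recruitment, Stage 2): "Therapists who have completed the BOOST MOOC will be invited to participate in a cohort study to evaluate patient outcomes". That section asks therapists to finish within six weeks of registering, but does not define completion or say who checks it. The Stage 2 primary objective in section 4.2 concerns patients' walking capacity "when delivered by therapists that have received the BOOST training online via the BOOST MOOC", and section 5.1 makes the online course the only training route in Stage 2.

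Section 8.2 analyses therapist outcomes descriptively, with listwise deletion of cases that have missing values.

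**The concern.** Having taken the course is the exposure that Stage 2 is about. Its only stated measurement is a survey item answered by the person whose performance is in question, in a study run by the team responsible for the course. Two consequences follow if some answers are too generous. The reported completion rate would be too high. And the patient results would be read as results of course-trained delivery although some of the deliverers had only part of the course.

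There is a second route to an inflated rate that needs no misreporting. Table 3 places the first completion question at the point of finishing the course, so a therapist who abandons it may never reach that survey. Listwise deletion would then remove that therapist from the denominator.

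**Working it through.** The protocol gives no completion rate, over-reporting rate or other figure that bears on this point, so there is nothing to reproduce. The check is a comparison of sections, followed by arithmetic that shows scale only.

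**Step 1: what verifies completion?**
- Section 6.1: self-report at the end of the course and at 6 months.
- Sections 6.1 and 9.6.2: surveys are the only stated source.
- Section 7.2: enrolment includes "instructions on how to create an account on FutureLearn", so each therapist has an individual account. No use of platform progress data is stated.
- Section 7.3 (MOOC evaluation): the information for therapists includes "informing them that their data will be shared with the BOOST study team". It does not say whether this covers platform data.
- Section 6.1 (Intervention fidelity): at least one individual and one group session are observed at each site against a checklist, and session, attendance, exercise and call logs are collected. These describe delivery and do not show who finished the course.

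No section names a check on completion other than self-report.

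**Step 2: what one misclassified therapist means for the patient cohort.** Section 8.1 gives minima of 60 patients and 10 therapists: 60 / 10 = 6 patients per therapist, and 6 / 60 = 10% of the cohort.

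**Step 3: chance that at least one of 10 admitted therapists had not finished.** With an assumed share q of non-finishers among those admitted, the chance is 1 − (1 − q)^10, treating therapists as independent.

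| q (assumed) | chance |
|---|---|
| 5% | 1 − 0.95^10 = 40% |
| 10% | 1 − 0.90^10 = 65% |
| 20% | 1 − 0.80^10 = 89% |

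**Step 4: effect on the reported rate.** Let p be true completion and o the share of non-finishers who say they finished, both assumed. Reported completion is p + (1 − p)o. The false share among claimed completers is (1 − p)o / [p + (1 − p)o].
- p = 0.5, o = 0.2: reported 0.5 + 0.5 × 0.2 = 60%; false share 0.10 / 0.60 = 17%.
- p = 0.7, o = 0.1: reported 0.7 + 0.3 × 0.1 = 73%; false share 0.03 / 0.73 = 4%.
- p = 0.3, o = 0.3: reported 0.3 + 0.7 × 0.3 = 51%; false share 0.21 / 0.51 = 41%.

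**Step 5: the denominator.** Suppose every answer is truthful and all finishers respond, but only a share r of non-finishers does. Completion among respondents is p / [p + (1 − p)r]. At p = 0.5 this is 50% if all non-finishers respond (r = 1) and 100% if none do (r = 0). The 6-month questionnaire is emailed by the study team and can reach non-finishers, so it can limit this effect to the extent that they reply.

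**The case against.** The strongest reply is that this is an openly labelled, pragmatic choice on which little depends. Completion is summarised descriptively. The Stage 2 benchmark in section 8.2 uses only patients' pain-related disability and walking. Some variation in training uptake is part of what an implementation study in routine practice observes. The incentive to overstate also looks weak: full course access comes with enrolment, section 9.9 states that no one is paid, and no penalty for not finishing is stated. A therapist who gave up on the course may well not go on to run a 12-week programme. Most of this stands, and it limits the weight of the point. It does not supply a check on completion.

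Three stronger readings are tempting and are not supported.
- A reader might infer that completion is overstated. The protocol contains no data on over-reporting, so only the possibility can be claimed. The 4% to 41% span in the working reflects its assumptions.
- A reader might infer that entry to the patient cohort is decided on self-report. Section 7.2 does not say so; it is silent on how completion is confirmed.
- A reader might infer that a poor Stage 2 result could not be told apart from poor training. The observation, checklist, logs and therapist interviews bear on whether delivery was adequate. They leave open whether the course was finished, and feedback after observation could correct gaps that incomplete training left.

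It is also fair that nothing in the protocol shows that the platform can release individual progress records. The fix therefore needs a fallback.

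**Conclusion.** The point holds in a limited form. Completion is a Stage 2 learning outcome measured only by self-report, and it is the entry condition for the patient cohort with no stated means of confirmation. The completion rate may be overstated, by generous answers or by loss of non-finishers from the denominator, and some patients may be treated by therapists who did not finish the course. The one figure that rests on the protocol's own numbers is that each such therapist would represent about 10% of the minimum cohort, assuming patients are spread evenly. How many there would be cannot be derived from the documents. Since completion enters no decision rule and delivery is checked separately, this is a worthwhile, inexpensive improvement of modest weight. It does not affect the sample size.

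**What to change.** - In section 6.1 and Table 3, define what counts as completion and take it from a record: the FutureLearn progress record if the platform can supply it, otherwise a completion certificate uploaded by the therapist.
- Report completion over all enrolled therapists, so that those who stop early or do not answer the survey stay in the denominator.
- In section 7.2, state that the record is confirmed before a delivering therapist enters the Stage 2 patient cohort.
- Keep the self-report item at both time points as a secondary measure.

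The cost is a small change to the therapist information sheet and consent form, with the related amendment under section 9.3.2. A platform or certificate record also adds an identifiable data link beside survey responses that section 9.6.2 describes as anonymised and joined by a unique ID, so that section needs a matching sentence. An occasional manual check will be needed for a therapist who studied the whole course but whose record does not show it. Patient procedures do not change.

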6 SAMPLE AND RECRUITMENT

Patient participants

7.1 Eligibility Criteria

Patients with symptomatic LSS.

7.1.1 Inclusion criteria

- Able to give informed consent
- Aged 65 years and over
- Symptoms include:
 - A report of back pain and/or pain or other symptoms such as tingling, numbness or heaviness that travels from their back into their buttocks or legs in the last 6 weeks.
 - o Standing or walking makes symptoms in the buttocks or legs worse.
 - Sitting or bending forward relieves symptoms.

Feedback from our COP members highlighted that insufficient numbers, or an inconsistent flow, of patients with symptomatic LSS, can result in long delays for the commencement of the group-based sessions. Thus, being pragmatic and cognisant of these important considerations, in stage 2 we will allow sites the flexibility to offer the BOOST programme to other older populations with back pain where the responsible therapist feels it would benefit the patient. In this situation, the same exclusion criteria would still apply, helping to ensure the patient is suitable for the group-based programme. These patients would still be invited to participate in the research study, completing the baseline and follow-up assessments.

7.1.2 Exclusion criteria

The participant may not enter the cohort study if ANY of the following apply:

- Nursing home resident.
- Inability to walk 3 meters independently.
- Awaiting surgery.
- Cauda equina syndrome or signs of serious pathology.
- Cognitive impairment (where applicable, the assessing physiotherapist will complete the Abbreviated Mental Test score, where the patient will need to score more than 6).
- Registered blind.
- Unable to follow instructions in a group setting.

Therapist participants

7.1.3 Inclusion Criteria

- Be either a qualified a health professional or a level 4 exercise therapist.
- Provide treatment (or plan to provide treatment in the near future) to patients with symptomatic lumbar spinal stenosis.

- Be based in the UK.
- Employed by either the NHS or a community health provider (depending on local business models, exercise therapists can be self-employed if they are providing services for a community provider).
- Aged 21 years and over.

7.1.4 Exclusion Criteria

Not meeting the inclusion criteria.

7.2 Recruitment Stage 1

Site recruitment

All physiotherapists who took part in the BOOST RCT will be contacted via email to inform them about an opportunity to participate in stage 1 and/or stage 2 of the BOOST programme optimisation and implementation. If this does not result in 4 NHS sites for stage 1, we will seek additional new sites (that did not participate in the BOOST RCT) based on our clinical networks. For 3 of the NHS sites, the BOOST programme will be delivered within the NHS as it was in the original RCT. For the forth NHS site, the BOOST programme will be delivered in the community with a local provider who has a good existing relationship with the NHS Trust.

We will conduct semi-structured interviews with all the therapists (n=4) delivering the optimised BOOST programme to understand the impact of the changes made to the programme.

Patient participant recruitment

Potentially eligible patients will be identified either from (i) physiotherapy waiting lists or (ii) from an initial consultation with a physiotherapist. Where identified from a waiting list, the patient will be sent the patient information sheet via post or email, depending on their preference, with a follow up phone call to ascertain if the patient would be interested in taking part. Where identified in an initial consultation with a physiotherapist, the physiotherapist will screen the patient for eligibility and provide the patient information sheet to the patient. Depending on the set up at each site, either a research physiotherapist in the NHS physiotherapy outpatient department, or the physiotherapist who conducted the initial consultation with the patient, will consent patients for the study, complete the study enrolment form (containing the participants contact details) and carry out the baseline assessment. For the site where BOOST will be delivered in the community, participants will be booked an individual appointment with the community provider to complete their baseline outcome measures and receive the first individual BOOST session. While the programme is running in the community, the referring physiotherapist will hold a consulting role, supporting the community provider as and when needed.

Stage 2

Therapist participant recruitment

Therapists who manage (or plan to manage) patients with symptomatic LSS in the UK will be invited to participate in a soft launch of the BOOST MOOC. This will not be publicly available, and therapists will need to agree to participate in the cohort study to gain access to it. We will target a minimum of 30 therapists and will recruit them through special interest groups and networks, conferences, University of Exeter, Keele and Oxford research group contact lists, Applied Research Collaboration regional websites, social media platforms, and personal contacts. Interested therapists will be asked to contact the BOOST study team to express their interest. Interested therapists will be sent a link to a webpage containing a participant information sheet, consent form and a baseline questionnaire prior to enrolment in the course. After providing informed consent and completing the baseline questionnaire, therapists

will be sent a link to enrol in the BOOST MOOC with instructions on how to create an account on FutureLearn. Once enrolled, therapists will have full access to the BOOST MOOC content. Therapists will be asked to complete the course within a six-week period from the date of registration.

Therapists who have completed the BOOST MOOC will be invited to participate in a cohort study to evaluate patient outcomes. We will target 10 NHS sites. Site can choose to deliver the BOOST programme within an NHS setting or to partner with a community provider for the delivery of the BOOST programme.

We will email the first 10 therapists to deliver the optimised BOOST programme in their practice to invite them to participate in a semi-structured interview.

Patient participant recruitment

Patient recruitment and study procedures are the same as those described in stage 1 above.

7.3 Consent

Stage 1 and 2: Patient Participants

The consent process will vary by site, depending on local staff and procedures. Patients will with be sent a patient information sheet by post or email or, provided with one during their initial consultation with a physiotherapist in clinic. With either route, written and verbal versions of the PIS and informed consent form (ICF) will be presented to patients detailing the exact nature of the cohort study, what it will involve for the patients, and how their data will be handled. Where patients have been sent the PIS via post/email, the departmental research physiotherapist or other member of the patient's clinical team will call them to discuss the PIS and answer any questions.

It will be clearly stated that the participant is free to withdraw from the cohort study at any time, for any reason, without prejudice to future care, and with no obligation to give the reason for withdrawal. Data contributed to the study up until the point of withdrawal will remain with the study group, unless stated by the withdrawing participant.

A copy of the signed ICF will be given to the participant, and one copy will be sent to the BOOST study team. The original signed form will be retained by the site in the Investigator Site File and a copy placed in the participant's medical notes. The participant's GP will be sent a letter by the study team, informing them of the participant's involvement in the cohort study.

Stage 1 and 2: Therapist Participants

Interviews

Therapists will be sent an invitation to take part in an online interview via an email containing the PIS and ICF. The PIS clearly states the nature of the study and that they are free to withdraw at any time, for any reason, and with no obligation to give a reason for withdrawal. Therapists will be offered the opportunity to ask any questions using the contact information provided. Interviews will be conducted via MS Teams and will be audio-video recorded and automatically transcribed. Those willing to take part will be asked to sign and return their consent form via email. On commencement of the interview, verbal consent will also be taken.

MOOC evaluation

Therapists expressing an interest in the BOOST MOOC will be emailed a link to a webpage containing the PIS and ICF, detailing the exact nature of the cohort study and informing them that their data will be shared with the BOOST study team. It will be clearly stated that the participant is free to withdraw from the cohort study at any time, for any reason, and with no obligation to give a reason for withdrawal. Data

contributed to the study up until the point of withdrawal will remain with the study group, unless stated by the withdrawing participant.

